1.1 SAP Version History / Summary of Changes

Version/Date	Summary of Changes

3 LIST OF ABBREVIATIONS AND DEFINITIONS OF TERMS

WHODrug W	Vorld Health Organization Drug Dictionary

Г

4 INTRODUCTION

The purpose of this statistical analysis plan (SAP) is to describe the planned analyses and reporting for clinical study Bausch & Lomb 884 conducted according to TENEO 317 Clinical Investigation Plan, Version 8.0, dated 19 November 2020.

This SAP is being written with due consideration of the recommendations outlined in the most recent International Conference on Harmonisation (ICH) E3 Guideline (July 1996), entitled Guidance for Industry: Structure and Content of Clinical Study Reports.

This SAP describes the data that will be analyzed and the subject characteristics, device effectiveness, and safety assessments that will be evaluated.

This SAP provides details of the specific statistical methods that will be used. The statistical analysis methods presented in this document will supersede the statistical analysis methods described in the clinical protocol. If additional analyses are required to supplement the planned analyses described in this SAP, they will be completed and will be identified in an amended SAP (approved prior to database lock) or in the clinical study report.

Device Description

The Technolas Teneo 317 Model 2 (ver. 1.28 US software [SW]) excimer laser is a scanning excimer laser that operates at 193 nm ultraviolet wavelength to photoablate corneal tissue and employs a proprietary aspheric ablation profile rather than a conventional "Munnerlyn" ablation profile. By scanning a small diameter beam (1 mm in diameter) in a random raster pattern, the Teneo 317 Model 2 (ver. 1.28 US SW) excimer laser offers the following advantageous features:

- Flexible treatment patterns for the treatment of myopia,
- Wide ablation zones (up to 7 mm), and
- A smooth ablation-surface.

5 STUDY OBJECTIVES

The primary objective of this clinical investigation is to collect safety and effectiveness data for the Technolas Teneo 317 Model 2 excimer laser for Laser-Assisted In Situ Keratomileusis (LASIK) correction of myopia and myopic astigmatism. It is intended that the results of the study will be submitted to the U.S. Food and Drug Administration (FDA) in a 180-day premarket approval (PMA) application supplement.

6 INVESTIGATIONAL PLAN

6.1 Overall Study Design

The design of this clinical study is a prospective, open-label, multicenter, non-randomized clinical investigation, where the effects of LASIK in correcting myopia and myopic astigmatism are evaluated by comparing postoperative refraction and visual acuity to performance standards. The study treatment range (indication for use) includes up to manifest refraction spherical equivalent (MRSE) of -11.50 diopters (D).

The study will involve an evaluation of approximately 334 treated eyes at up to 12 investigational sites, with a final sample size of at least 300 study eyes evaluable at the final visit. Every effort will be made to enroll approximately the same number of eyes at each investigational site. The additional 34 study eyes will allow for losses up to 10% due to early subject discontinuation. Both eyes of a subject may be enrolled. Subjects will be permitted to have both eyes enrolled so long as both eyes meet all inclusion/exclusion requirements. Analyses will include all enrolled eyes treated with the TENEO 317 laser. Enrollment will be limited to subject eyes with sphere of -1.0 D up to -10.00 D, cylinder between 0.0 D and -3.0 D, and with a spherical equivalent (SE) between -1.0 D and -11.50 D. Enrolled subjects can possibly attend up to 8 scheduled study visits. It is planned to enroll and treat approximately 334 subject eyes, with an expectation that approximately 300 study eyes will complete post-surgical follow-up for 9 months. All subjects, regardless of the time of individually achieving refractive stability, will be followed up until the last study visit (Visit 8) which is Month 9 postoperatively.

For completed subjects, it is planned to have ≥ 20 eyes per each dioptric bin (see **Table 1**) of spherical correction to be studied and ≥ 30 eyes per dioptric bin of cylinder correction

to be studied. Of the eyes in the -0.25 to -1.0 D astigmatism range, at least 30 eyes are planned to be in each of the -0.25 to -0.5 D and the -0.5 to -1.0 D astigmatism ranges (see **Table 1**, Bin Table).

A 180-Day PMA supplement application will be submitted to the U.S. FDA when the enrolled study cohort has completed approximately 9 months of safety and effectiveness assessments post-surgery.

Refractive Error Stratified by Manifest Sphere and Cylinder						
			Cylii	nder (in minus n	otation)	
	0 Cylinder (Sphere Only)	-0.25 to - 0.5 D	-0.51 to -1 D	-1.01 to -2 D	-2.01 to -3 D	Total
Sphere (in minus notation)	n	n	n	n	n	n
-1 to -2 D	> 0	> 0	> 0	> 0	> 0	≥ 20
-2.01 to -3 D	> 0	> 0	> 0	> 0	> 0	≥ 20
-3.01 to -4 D	> 0	> 0	> 0	> 0	> 0	≥ 20
-4.01 to -5 D	> 0	> 0	> 0	> 0	> 0	≥ 20
-5.01 to -6 D	> 0	> 0	> 0	> 0	> 0	≥ 20
-6.01 to -7 D	> 0	> 0	> 0	> 0	> 0	≥ 20
-7.01 to -8 D	> 0	> 0	> 0	> 0	> 0	≥ 20
-8.01 to -9 D	> 0	> 0	> 0	> 0	> 0	≥ 20
-9.01 to -10 D	> 0	> 0	> 0	> 0	> 0	≥ 20
Total	≥30	≥30	≥30	≥ 30	≥ 30	≥ 300

Table 1. LASIK Preoperative 'Dioptric Bin' Enrollment Plan

6.1.1 Fellow Eye Treatments

Because unilateral enrollment would result in subjects with a significant degree of anisometropia, and the safety and effectiveness of the TENEO 317 Model 2 excimer laser (ver. 1.28 US SW) specific to the treatment of myopia or myopic astigmatism are supported by retrospective data, bilateral LASIK treatments will be permitted in this study. Both eyes may be enrolled for effectiveness and safety assessments if the subject is fully informed that the surgical risks apply equally to each eye. If an intraoperative complication or adverse

event (AE) occurs in the first eye, treatment must be abandoned in the second eye. Each eye treated according to this protocol for an enrolled subject will be reported separately and included in the data analysis.

6.1.2 Enhancement and Retreatment Procedures

If the treated eye remains under-corrected and/or corneal haze or vision regression decreases to an uncorrected distance visual acuity (UCDVA) of 20/30 or worse, then an enhancement or retreatment may be performed. No enhancement or retreatment may be performed before a subject exits the study. Therefore, no data analysis related to enhancement or retreatment is planned.

6.1.3 Scheduled Visits

The schedule of visits and parameters is presented in **Table 2** below. All study tasks must be performed by qualified study site personnel as indicated on the delegation of authority log under the supervision of the Principal Investigator.

Further detail for scheduled visit procedures can be found in the study protocol.

	Visit 1	Visit 2	Visit	Visit	Visit	Visit	Visit	Visit
			3	4	5	6	7	8
	Pre-Op	Operative						
Test	(Day-60	Visit	Day	Week	Month	Month	Month	Month
	to Day -1)	(Day 0)	1	1	1	3	6	9
	• /			(Day	(Week	(Week	(Week	(Week
				5-9)	3-5)	10-14)	21-26)	35-43)
Informed Consent/HIPAA	Х							
Eligibility	Х	Х						
PROWL Questionnaire	Х					Х	Х	Х
Adverse Events	Х	Х	Х	Х	Х	Х	Х	Х
Complications		Х	Х	Х	Х	Х	Х	Х
Subject Demographics	Х							
Medical/Ocular History	Х							
Concomitant Medications	Х	Х	Х	Х	Х	Х	Х	Х
Schirmer's Test	Х						Х	
LASIK Surgery,		Х						
Intraoperative Events		Λ						
Manifest Refraction	Х			Х	Х	Х	Х	Х
Keratometry	Х							
Endothelial Cell Density (ECD)	Х						Х	
Corneal Topography	Х				Х	Х	Х	Х
Pupil Size	Х					Х	Х	Х
UCNVA	Х		Х	Х	Х	Х	Х	Х
UCDVA	Х		Х	Х	Х	Х	Х	Х
Distance BSCVA	Х			Х	Х	Х	Х	Х
Contrast Sensitivity	Х						Х	
Slit Lamp Examination	Х		Х	Х	Х	Х	Х	Х
Pachymetry	Х							
Cycloplegic Refraction	Х							
Intraocular Pressure	Х				Х	Х	Х	Х
Dilated Fundoscopic	Х					Х	Х	Х
Examination	Λ					Λ	Λ	л

Table 2. Schedule of Visits and Parameters

6.2 Selection of Study Population

The subject must satisfy all eligibility criteria prior to enrollment. The subject is considered enrolled in the study at the time they sign the informed consent form, with the study eye selected by the Investigator at the first study visit (Preoperative). It is understood that the number of subject eyes enrolled at the first study visit may be slightly more or less than the target number of 334 treated eyes.

Subjects failing to meet eligibility criteria prior to scheduling of surgery are considered screen failures.

- 6.2.1 Inclusion Criteria
 - 1. Are 22 years of age or older.
 - 2. Have read, understood, and signed an informed consent form (ICF).
 - 3. Have demonstrated stable refraction (i.e., a change of ≤ 0.5 D in sphere and cylinder) for a minimum of 12 months prior to surgery, verified by consecutive refractions and/or medical records or prescription history.
 - 4. Have myopic refractive error with or without astigmatism; sphere between -1.0 D and -10.00 D, cylinder between 0.0 D and -3.0 D; with a manifest refraction spherical equivalent (MRSE) between -1.0 D and -11.50 D.
 - 5. Have UCDVA of 20/40 or worse.
 - 6. Have manifest best spectacle corrected distance visual acuity (BSCVA) of 20/25 (logarithm of the minimum angle of resolution [logMAR] 0.1) or better in an operative eye.
 - 7. Have less than or equal to 0.50 D SE difference between cycloplegic and manifest refractions at Visit 1 (Preoperative).
 - 8. Have normal corneal topography as determined by the Investigator.
 - 9. Have discontinued use of contact lenses for at least 2 weeks (for hard or toric lenses) or 3 days (for soft contact lenses) prior to the preoperative examination, and through the day of surgery.
 - 10. All contact lens wearers must demonstrate a stable refraction (within \pm 0.5 D), as determined by MRSE, on two consecutive examinations at least 1 week apart, in an eye to be treated and the axis of cylinder should not differ by more than 15 degrees.
 - 11. Have the ability to lie flat without difficulty.
 - 12. Are willing and able to comply with the schedule for all post-surgery follow-up visits.

6.2.2 Exclusion Criteria

- Subjects for whom the combination of their baseline corneal thickness and the planned operative parameters for the LASIK procedure would result in treatment depth less than 250 microns from corneal endothelium.
- 2. Eyes for which the baseline manifest subjective refraction exhibits a difference greater than 0.50 D in sphere power, or a difference greater than 0.50 D in cylinder power, or a difference in cylinder axis of more than 15 degrees compared to the baseline cycloplegic subjective refraction. For manifest cylinder of less than 0.50 D, the difference in cylinder axis will not be taken into consideration.
- 3. Subjects for whom the preoperative assessment of the cornea indicates that one or both eyes are not suitable candidates for treatment based upon the Investigator's medical judgment.
- 4. Have evidence of retinal vascular disease.
- 5. Have a history of or have active corneal disease or infection (e.g., recurrent corneal erosion syndrome, herpes simplex or herpes zoster keratitis, etc.) in an eye.
- 6. Have a known sensitivity to any study medication.
- 7. Have central corneal scars affecting visual acuity or unstable keratometry with irregular mires in an eye considered for eligibility.
- 8. Have keratoconus, subclinical or forme fruste keratoconus, corneal dystrophy, or other corneal irregularity (e.g., irregular astigmatism).
- 9. Have visually significant or progressive cataract in an eye considered for eligibility.
- 10. Had previous intraocular or corneal surgery in an eye considered for eligibility that might confound the outcome of the study or increase the risk to the subject.
- 11. Use chronic medications by any administration route that may increase risk to the subject or may confound the outcome of the study, including those known to affect wound healing (e.g., corticosteroids, antimetabolites, etc.).
- 12. Are known to have acute or chronic disease or illness (e.g., dry eye, cataract, glaucoma, immuno-compromised, rheumatoid arthritis, clinically significant atopic disease, acne rosacea, etc.) that would increase operative risk or may confound the results of the study.
- 13. Are taking medications contraindicated for LASIK such as isotretinoin (Accutane) or amiodarone hydrochloride (Cordarone).
- 14. Are known to be pregnant, lactating, or who plan to become pregnant during the course of the study.
- 15. Have known sensitivity to medications used for standard LASIK.

- 16. Have the presence of systemic disease likely to affect wound healing, e.g., autoimmune disease, systemic connective tissue disease, diabetes, or severe atopic disease.
- 17. Are participating in any other ophthalmic clinical trial within 30 days of screening or during this clinical trial.
- 18. Have an ocular muscle disorder including a strabismus or nystagmus, or other disorder affecting fixation.
- 19. Have a history of or evidence of glaucoma or are a glaucoma suspect.
- 20. Have eyes with mesopic pupil size > 7.0 mm.
- 21. Have a Schirmer's preoperative test without anesthesia < 4 mm/5 minutes.

6.3 TENEO 317 Model 2 Excimer LASIK Laser Device (Treatment Device)

Eligible subjects will undergo a LASIK surgical procedure with the TENEO 317 Model 2 (ver. 1.28 US SW) excimer laser device on one or both eyes.

6.4 Effectiveness and Safety Variables

The following endpoints will be evaluated.

6.4.1 Effectiveness Variables

Data for the following primary effectiveness endpoints will be evaluated statistically at the achievement time for refractive stability. Since the time of achievement for refractive stability cannot be predicted *a priori*, the effectiveness endpoints will be evaluated at 1-month, at 3 months, and at 6 months. In the absence of refractive stability occurring by 6 months post-surgery, the primary effectiveness endpoints will also be evaluated at 9 months post-surgery.

6.4.1.1 Primary Effectiveness Endpoints

The primary effectiveness endpoints are:

- The percentage of eyes that achieve predictability of MRSE within ± 0.50 D;
- The percentage of eyes that achieve predictability of MRSE within \pm 1.00 D; and
- The percentage of eyes targeted for emmetropia that achieve a UCDVA of 20/40 or better.

6.4.1.2 Secondary Effectiveness Endpoints

There are no secondary effectiveness endpoints.

6.5 Statistical Methods

6.5.1 Disposition of Subjects

Eye accountability will be presented by postoperative visit separately for all treated eyes, eyes treated for spherical myopia, and eyes treated for astigmatic myopia. The numbers and percentages of subjects who were available for analysis, discontinued from the study, ongoing, lost to follow-up, or missed the visit will be displayed. Percent accountability, defined as eyes available for analysis divided by (enrolled minus discontinued minus active eyes) will also be presented by visit.

The reasons for premature study discontinuation will not be summarized but will be listed. In addition, subject data listings will be provided that include exclusions from study populations and any inclusion and exclusion criteria violations.

6.5.2 **Protocol Deviations**

Protocol deviations will not be summarized but will be presented in a data listing.

As required under §21 CFR 56.108(a)(3) & (4), an Investigator should notify the Sponsor and reviewing Institutional Review Board (IRB) of any deviation from the investigational plan intended to protect the life or physical well-being of a subject in an emergency. The date of and reason for protocol deviations will be documented in all cases. Significant or major protocol deviations affecting the safety, rights, and welfare of the subject or the integrity of the study must be reported by the Investigator to the IRB immediately. Reporting of all other protocol deviations must adhere to the requirements of the governing IRB.

Protocol assessments will continue until the end of the study, unless the protocol deviations put the subject at risk or the subject's condition requires that he/she should be discontinued from the study.

Protocol deviations related to Coronavirus Disease 2019 (COVID-19) pandemic impact on assessments described in the protocol will be presented in a separate data listing.

6.5.3 Data Sets Analyzed

6.5.3.1 Study Population

All subjects will be analyzed as enrolled in the following study populations.

- All Treated Eyes: All eyes enrolled and treated with the TENEO 317 model 2 excimer-laser,
- All Eyes Treated for Spherical Myopia,
- All Eyes Treated for Astigmatic Myopia,
- All Treated Eyes with Low to Moderate (> -7 D MRSE) Preoperative Myopia, and
- All Treated Eyes with High (<= -7 D MRSE) Preoperative Myopia
- Consistent Cohort (cohort of eyes that have every postoperative visit from 1 month up to the stability visit).

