7.1.2.2 Surgical Technique

Eligible subjects will undergo a LASIK surgical procedure with the TENEO 317 Model 2 (ver. 1.28 US SW) excimer laser device on one or both eyes. In no case should a concurrent bilateral procedure be attempted if there are problems or complications during the surgical procedure for the initial subject eye. The minimum diameter of the optical zone, the degree

of myopia and the magnitude and axis of the astigmatic correction are all determined by the surgeon based on the subjective manifest refraction and mesopic pupil size. The typical optical zones used for TENEO 317 Model 2 (1.28 US) laser treatments of myopia or myopic astigmatism performed outside of the US have been approximately between 6.0 mm and 7.0 mm; however, the 1.28 US software will permit treatments of mesopic pupil sizes within the range of 4.5 mm to 7.0 mm. Operator attempts to enter an OZ size outside this range results in a prompt, "out of range". If the corneal flap created is smaller than the treatment zone size, the procedure will be cancelled. The default treatment parameters (K = 43.3 D, Q = -0.20), not the measured pre-operative keratometry (K) and asphericity (Q) values, will be manually entered into the Teneo 317 Model 2 (ver. 1.28 US SW) excimer laser system. This information is used to develop a laser ablation pattern that removes tissue based on an aspheric algorithm, and additional peripheral tissue removal necessary to achieve the desired post-operative corneal surface asphericity.

Treatment plans for all eyes undergoing LASIK surgery are strongly recommended to be targeted for emmetropia

For expected residual postoperative cylindrical refractive error of ≥ 1.0 D or spherical refractive error of ≥ 2.0 D, the subject should be given the opportunity to experience his/her best spectacle vision with anticipated correction only and be willing to proceed with the surgery.

Details of the surgical technique are described in Appendix C.

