9.5 Study Population

All eyes enrolled and treated with the TENEO 317 model 2 excimer laser will constitute the Study Population.

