2.0 LASIK SURGICAL TECHNIQUE

The surgical technique consists of ablating tissue from the stroma after having created a flap of corneal tissue with a femtosecond laser. The flap is folded back exposing the central cornea where the excimer laser will ablate the stromal tissue. The shape of the ablated area for myopia is achieved by allowing more laser pulses to strike the central than the peripheral portion of the ablation area. The shape of the ablated area for astigmatism is achieved by allowing more laser pulses to strike the flatter axis of the cornea. The surgery performed, and particularly the size of the optical zone, will be determined by needed refractive correction of the patient, the pupil size, the central pre-operative corneal thickness (as measured by pachymetry), flap thickness and amount of residual corneal tissue (residual corneal thickness should be no less than 250 microns).

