6.5.8.3 Adverse Events and Unanticipated Adverse Device Effects

An AE is defined as any untoward medical occurrence, unintended disease or injury, or untoward clinical signs (including abnormal laboratory finds) in subjects, users, or other persons, whether or not related to the investigational medical device.

The following AEs are the key safety events surveilled during the study in order to assess conformity to the target values of "Incidence of Adverse Events".

- Loss of > 2 lines (10 letters) BSCVA
- BSCVA worse than 20/40
- BSCVA worse than 20/25 if 20/20 or better preoperatively
- Haze \geq trace with loss of BSCVA > 2 lines (10 letters)
- Increased manifest refractive astigmatism > 2.0 D
- Corneal epithelial defect involving the keratectomy at one month or later
- Melting of the flap
- Miscreated flap (lost, incomplete, too thin)
- Diffuse lamellar keratitis (Grade 3 or above)
- Corneal infiltrate or ulcer

- Any persistent corneal epithelial defect at one month or later
- Epithelium in the interface with loss of 2 lines (10 letters) or more BSCVA
- IOP with increase of > 10 mmHg above baseline on two consecutive examinations or an IOP greater than 30 mmHg on two consecutive examinations
- Haze beyond 6 months with loss of 2 lines or greater (≥ 10 letters ETDRS) of BSCVA
- Decrease in BSCVA of greater than or equal to 2 lines (≥ 10 letters ETDRS) not due to irregular astigmatism as shown by rigid contact lens refraction at 3 months or later
- Retinal detachment
- Corneal edema at 1 month or later
- Retinal vascular accidents
- Ocular penetration
- Other ocular event

All UADEs are considered to be rare, unanticipated events and have a serious effect on health or safety or represent any life-threatening problem or death caused by the device, if the event has not previously been identified in the investigational plan. A UADE may include, but is not limited to, the following events:

- Device-related death
- Enucleation of treated eye
- Corneal transplant of treated eye

A summary (counts and percentages) of AEs/UADEs will be presented by incidence of AEs for operative visit, each postoperative study visit, and overall (a Total column) using all treated eyes. At a study visit subjects' eyes will be counted only once if they experience multiple AEs/UADEs of the same type and similarly will be counted only once in Total column if they have AEs/UADEs of the same type at multiple study visits.

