6.5.8.4 Complications/Potential Adverse Events

Complications/Possible AEs are known to potentially occur in association with laser refractive surgery and include the safety events listed below:

- Allergic conjunctivitis
- Blepharitis
- Conjunctivitis
- Corneal abrasion
- Corneal edema between 1 week to less than 1 month after procedure
- Corneal flap lifting between 1 day to 1 month post-surgery for wrinkled flap
- Corneal haze
- Corneal scar
- Debris in the interface
- Diffuse lamellar keratitis (grade 2 or less)
- Double/ghost images in operative eye
- Dry eye
- Enhancement not done due to flap fibrosis
- Epithelium at the flap edge
- Epithelium in the interface
- Flap is not of the size and shape as initially intended or resultant flap is misaligned
- Foreign body sensation at 1 month or later
- Iritis
- Loose epithelium
- Meibomian gland dysfunction

- Mucus under edge of flap
- Pain at 1 month or later
- Peripheral corneal epithelial defect at 1 month or later
- Possible allergic reaction to plugs or eye drops
- Postoperative flap complications
- Punctal plug inserted
- Punctal plug replaced
- Rough epithelium
- Superficial punctate keratopathy (SPK)
- Steroid induced IOP increase
- Subconjunctival hemorrhage
- Transient light-sensitivity syndrome (TLSS)
- Trace microstriae
- Trace corneal haze
- Vitreous floaters
- Other

Complications/potential AEs will be summarized in a similar manner as AEs/UADEs for operative visit, each postoperative visit, and overall (a Total column) using all treated eyes.

All complications/potential AEs also will be presented in a data listing by subject. The complications/potential AEs leading to study discontinuation will be listed separately.

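### An eye whose surgery is cancelled after the flap is cut, before any excimer pulse, falls outside the AE and complication tables, and no table counts aborted procedures

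*SAP*

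**What the plan says.** **Who is counted.** SAP 6.5.3.1 defines the main set as "All Treated Eyes: All eyes enrolled and treated with the TENEO 317 model 2 excimer-laser". Protocol 9.5 is equivalent: "All eyes enrolled and treated with the TENEO 317 model 2 excimer laser will constitute the Study Population". Neither document says what makes an eye *treated*.

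**Which tables use that set.** SAP 6.5.8.3 presents adverse events "for operative visit, each postoperative study visit, and overall (a Total column) using all treated eyes". SAP 6.5.8.4 follows suit: "Complications/potential AEs will be summarized in a similar manner as AEs/UADEs for operative visit", again on all treated eyes.

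**Order of surgery.** Protocol Appendix C, section 2.0, describes "ablating tissue from the stroma after having created a flap of corneal tissue with a femtosecond laser". Protocol 6.3.1.1 lets sites use any commercially available femtosecond laser for the flap. The flap step therefore does not use the test device.

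**How an eye can have a flap and no ablation.** Protocol 7.1.2.2 states: "If the corneal flap created is smaller than the treatment zone size, the procedure will be cancelled". There is a second route. Appendix C, section 4.0, lets the surgeon cut both flaps before ablating either eye, and Protocol 5.2.1 requires the second eye to be abandoned after an intraoperative complication or adverse event in the first.

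**What is collected and reported.** The operative report (Protocol 7.1.2.3) records whether a procedure was aborted. SAP 6.5.1 has no aborted category in its accountability table, and SAP 6.5.4.4 lists operative variables without summarising them. Protocol 9.6.3.3 plans a separate summary of how often flaps were miscreated. SAP 6.5.8 does not carry it over, and SAP 6.6 does not mention its removal.

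**The concern.** The event that stops the ablation also removes the eye from the table meant to count that event. The cancellation rule in Protocol 7.1.2.2 corresponds closely to a listed complication: "Flap is not of the size and shape as initially intended or resultant flap is misaligned". An eye cancelled for that reason would be missing from both numerator and denominator, even in the operative-visit column.

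The error can go in one direction only: the tabulated number of flap events equals the true number or falls below it. Because the rates are low, a few missing eyes matter relative to what is shown. A reader of the tables also could not tell whether any ablation was cancelled.

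The miscreated-flap row is among the adverse events of which SAP 6.5.8.3 says: "The following AEs are the key safety events surveilled during the study in order to assess conformity to the target values". That row is affected only if a lost, incomplete or thin flap also leads to an aborted procedure.

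**Working it through.** **Inputs.** Planned treated eyes: 334, for 300 evaluable after 10% loss (Protocol 9.3.5, SAP 6.5.9.5). Check: 300 / 0.90 = 333.3, rounded up to 334, which agrees. The documents give no abort rate, so every abort and event count below is an assumption.

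**Step 1: place the cancelled eye.**
- The flap exists, so surgery has begun. Protocol 5.3.4 treats withdrawal before surgery as screen failure and says that subjects discontinued during or after surgery are not replaced. It gives no analysis set for the second group.
- No excimer pulse was delivered, so on the plain reading the eye is not in All Treated Eyes.
- Both safety tables use All Treated Eyes, so the eye is in neither.

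**Step 2: formulae.** Let f = eyes with a flap event among 334 ablated eyes, a = further eyes aborted after flap creation started, and e = aborted eyes with a flap event.
- Rate shown in the tables: f / 334
- Rate among eyes with flap creation started: (f + e) / (334 + a)
- Intervals: exact (Clopper-Pearson) two-sided 95%. With zero events the upper limit is 1 − 0.025^(1/n), which for n = 334 is 1.10%.

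**Step 3: results with a = e.**

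| Aborted for a flap event | Shown, f = 0 | Flap-started, f = 0 | Shown, f = 3 | Flap-started, f = 3 |
|---|---|---|---|---|
| 0 | 0/334 (0 to 1.10%) | 0/334 (0 to 1.10%) | 3/334 = 0.90% | 3/334 = 0.90% |
| 1 | 0/334 | 1/335 = 0.30% (0.01 to 1.65%) | 3/334 = 0.90% | 4/335 = 1.19% |
| 3 | 0/334 | 3/337 = 0.89% (0.18 to 2.58%) | 3/334 = 0.90% | 6/337 = 1.78% |
| 5 | 0/334 | 5/339 = 1.47% (0.48 to 3.41%) | 3/334 = 0.90% | 8/339 = 2.36% |

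The two columns headed *Shown* do not change however many eyes are aborted.

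**Step 4: which row loses the events.** Take 3 aborted eyes and f = 0, and let k of the 3 meet the miscreated-flap definition. The adverse event row should then be k/337 (0, 0.30, 0.59 or 0.89% for k = 0 to 3) and the complication row (3 − k)/337. Both are shown as 0/334.

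**Step 5: sensitivity.**
- If aborted eyes come out of the 334 instead of on top of it, 3 aborts give 3/334 = 0.90% (0.19 to 2.60%) against 0/331 shown, with upper limit 1 − 0.025^(1/331) = 1.11%. The picture is the same.
- An eye cancelled without any flap event hardly matters: 3/334 = 0.898% against 3/335 = 0.896%.

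**The case against.** The strongest reply is that the population is a reasonable choice. The test device is the excimer laser, and an eye never exposed to it says nothing about the safety of ablation. That stands, and it is why the existing tables should keep their denominator. It does not explain why flap events, which the plan chooses to tabulate for the operative visit, should be counted only when they did not stop the surgery.

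A second reply is that cancelled eyes can be found in listings: exclusions from study populations (SAP 6.5.1), problems during surgery (6.5.4.4), and all adverse events and complications (6.5.8.3, 6.5.8.4). This stands in part. SAP 6.5.6.1 bases listings on treated subjects unless otherwise specified, so a subject with no ablated eye may not appear. A listing also gives no rate.

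A third reply is that *treated* could mean surgery begun, in which case nothing is lost. That reading is possible, but neither document states it.

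A reader might also infer more than the documents support:
- *That miscreated flaps are no longer tabulated.* They are: miscreated flap remains a row of the adverse event table in SAP 6.5.8.3. Only the protocol's separate, largely duplicate summary is gone. Its absence from SAP 6.6 is a gap in the record, since 6.6 does log bullets dropped for redundancy and the Schirmer's table.
- *That the SAP narrowed the protocol's population.* It did not, because Protocol 9.5 has the same limit. Reinstating the protocol's bullet alone would not bring cancelled eyes in.

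**Conclusion.** The concern holds as a gap in the safety tables. On the plain reading of *treated*, a flap event that prevents ablation is not counted, and no table reports aborted procedures. The possible undercount has a known direction but an unknown size. It is zero if no procedure is cancelled after flap creation starts or if *treated* is read as surgery begun. With 1 to 5 such eyes, and none among 334 ablated eyes, a rate shown as 0% with upper limit 1.10% would become 0.30% to 1.47%, with upper limits of 1.65% to 3.41%.

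It would be wrong to read this as a threat to the trial's main conclusions. No effectiveness hypothesis is affected. The rate of serious device-related events is hardly touched, because the flap laser is not the test device. The comparison with adverse event targets changes only if a lost, incomplete or thin flap also led to an abort. The change is nevertheless worth making, because it is cheap and the present tables cannot answer the question.

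**What to change.** 1. In SAP 6.5.3.1, define *treated*, and add a supplementary safety set of all eyes in which flap creation was started.
2. Add one separate table on that set. It should give the number of aborted procedures with reason, and all flap-related adverse events and complications. Include miscreated flap and any later flap-related event recorded in an aborted eye.
3. State that the adverse event and complication listings include these eyes.
4. In SAP 6.6, record the new set and how the protocol's miscreated-flap summary is handled.
5. Leave the existing adverse event, complication and effectiveness tables on excimer-treated eyes, so that no table mixes denominators.

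**Cost.** SAP wording, one derived flag and one extra table. The flap-event rate may look slightly less favourable. The operative report already records aborted procedures and operative flap complications, but not explicitly the stage reached, so that may have to come from the abort reason or the source record. Protocol 7.1.3 specifies scheduled postoperative event recording for treated eyes. Later events in aborted eyes may therefore be incompletely captured, and the new table should say so in a footnote.
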